### *Research Design and Methodology*

In this prospective cohort study, participants referred for a sleep study by in-lab polysomnography at the Jordan University Hospital and those who preferred their study conducted at a private clinic or by at-home sleep study will be screened and physically examined for any facial discoloration which will be accordingly graded as low, moderate, or high based on severity of difference from normal skin color and texture and pictured with patients' consent and privacy maintained. In addition to a general history, participants will be asked in detail about their smoking habits, vasovagal symptoms, sleeping habits, and any specific obstructive sleep apnea symptoms. After the sleep study is performed, positive and negative results will be collected and correlated with presence of facial discolouration. Severity of OSA will be graded by apnea-hypopnea index (AHI) and recorded as mild (5 - 15 events/hour), moderate (15 - 30 events/hour), or severe (> 30 events/hour). Participants with positive results will then be followed up with at 3 weeks and 6 months to determine what treatment they were given, assessed for improvement on treatment, and be questioned regarding smoking and vasovagal symptoms again. Improvement is defined as better sleep quality and reduction of initial symptoms. Participants with negative results will also be followed up with and asked about their smoking habits and vasovagal symptoms. Correlation will then be made between the group that improved on treatment and the group that did not (whether due to ineffective treatment or not receiving treatment at all) to see if improvement reduces smoking tendency with alleviated vasovagal symptoms, and compared with participants with negative sleep study results for any change in smoking habits as well.

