### *Data Collection*

Researchers will interview patients in person at their initial sleep study visit to physically examine and observe participants' faces for discoloration and take pictures for future reference with consent. Follow up at 3 weeks and 6 months will be done either in the clinic or over the phone and Email.

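### The protocol asks whether improvement reduces smoking but does not require improvement to come before the smoking change, so the stated comparison cannot separate the two directions

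*Protocol*

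**What the plan says.** All the relevant text is in the protocol, mostly under Research Design and Methodology.

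- **Baseline.** At entry "participants will be asked in detail about their smoking habits, vasovagal symptoms, sleeping habits, and any specific obstructive sleep apnea symptoms", so a change in smoking can be calculated later.
- **Follow-up.** "Participants with positive results will then be followed up with at 3 weeks and 6 months to determine what treatment they were given". At these contacts they are also to be "assessed for improvement on treatment, and be questioned regarding smoking and vasovagal symptoms again". The Data Collection section repeats the two times: "Follow up at 3 weeks and 6 months will be done either in the clinic or over the phone and Email".
- **Definition of improvement.** "Improvement is defined as better sleep quality and reduction of initial symptoms". No contact is named at which this status is fixed.
- **Comparison.** "Correlation will then be made between the group that improved on treatment and the group that did not". The second group explicitly includes people who had no treatment as well as those whose treatment did not work.
- **Question.** The comparison is made "to see if improvement reduces smoking tendency with alleviated vasovagal symptoms". Participants with a negative sleep study are a further comparison group for change in smoking.

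**The concern.** The question has a direction: improvement first, less smoking afterwards. The grouping used to answer it has no time order. Improvement is not assigned. It is a status that arises after baseline, rests on sleep quality and symptoms, and is asked about at the same contacts as smoking.

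Suppose a treated participant cuts down in the first week and reports better sleep at 3 weeks. Under the stated grouping this person is improved, with reduced smoking, and so supports the hypothesis even if the reduction came first and contributed to the better sleep.

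At stake is the reading of the smoking result. A difference between the groups would be compatible with improvement leading to less smoking, with less smoking leading to reported improvement, or with both. The sleep-study-negative group does not help, because no improvement status is defined for it.

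**Working it through.** **Text check.** Four things would put improvement before the smoking change. None is in the protocol.

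| What would give a time order | In the protocol? |
|---|---|
| A named contact at which improvement is classified | No |
| A requirement that improvement precede the smoking change | No |
| A lagged comparison (improvement at one contact, smoking change after it) | No |
| Dating of when either change began | No |

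The three measurement times (baseline, 3 weeks, 6 months) would permit a lagged comparison. The gap is therefore in the stated comparison and is not forced by the visit schedule.

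**Illustration of size.** The protocol gives no sample size, effect size or expected rates, so there is no figure of its own to reproduce. Every value below is an assumption.

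- Improvement has no effect on smoking.
- c = share who cut down early for other reasons = 0.20.
- t = share treated, unrelated to smoking = 0.50. Untreated participants count as not improved, as the protocol's grouping has it.
- q0 = chance of improving on treatment without cutting down = 0.50.
- q1 = the same chance after cutting down = 0.70, or 0.60 in a milder case.

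Formulas:

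- Share who cut down among the improved = t·c·q1 / [t·c·q1 + t·(1−c)·q0]
- Share who cut down among the not improved = (c − t·c·q1) / [1 − t·c·q1 − t·(1−c)·q0]

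With q1 = 0.70:

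- Improved and cut down: 0.5 × 0.2 × 0.7 = 0.07
- Improved and did not cut down: 0.5 × 0.8 × 0.5 = 0.20
- Among the improved: 0.07/0.27 = 25.9%
- Among the not improved: (0.20 − 0.07)/(1 − 0.27) = 0.13/0.73 = 17.8%
- Gap: 8.1 points

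With q1 = 0.60:

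- Among the improved: 0.06/0.26 = 23.1%
- Among the not improved: 0.14/0.74 = 18.9%
- Gap: 4.2 points

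With q1 = q0 = 0.50 (no reverse effect):

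- Among the improved: 0.05/0.25 = 20%
- Among the not improved: 0.15/0.75 = 20%
- Gap: 0

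**Sensitivity to c**, with t = 0.50 and q0 = 0.50:

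| c | q1 = 0.60 | q1 = 0.70 |
|---|---|---|
| 0.10 | 0.03/0.255 − 0.07/0.745 = 2.4 points | 0.035/0.26 − 0.065/0.74 = 4.7 points |
| 0.20 | 4.2 points | 8.1 points |
| 0.30 | 0.09/0.265 − 0.21/0.735 = 5.4 points | 0.105/0.28 − 0.195/0.72 = 10.4 points |

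**Sensitivity to t.** If everyone were treated (t = 1, c = 0.20), the gaps would be 0.14/0.54 − 0.06/0.46 = 12.9 points and 0.12/0.52 − 0.08/0.48 = 6.4 points. Counting untreated participants as not improved dilutes the effect, because some who cut down then fall in that group.

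**The case against.** **The protocol leaves the timing open; it does not fix a wrong one.** This is right as far as it goes. A reader might infer that the plan compares improvement and smoking from the same contact. It does not say so: both are asked at both contacts, and which contact's improvement is set against which contact's smoking is not stated. Setting 3-week improvement against 6-month smoking would be compatible with the text.

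**The lag belongs in the statistical analysis plan.** A plan that is not shown might supply one. But the protocol itself forms the groups and attaches a directional question to them. Followed as written, the comparison does not answer that question, and this does not depend on the analysis plan.

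**The group is those who improved on treatment.** This stands. An untreated smoker who cuts down and feels better is counted as not improved, with reduced smoking, which is evidence against the hypothesis. Only treated participants can produce the false support, and the calculation allows for this.

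**The reverse effect is assumed.** This also stands. A reader might conclude that the comparison would show less smoking in the improved group even with no true effect. The protocol gives nothing on the sign or size of any effect of cutting down on reported sleep, so the most that can be said is that it could.

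**The protocol only poses a question, in an observational cohort.** That is fair, and it draws no causal conclusion in advance. The question is still directional, and a cheap step would bring the comparison closer to it.

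**Conclusion.** The point holds in a limited form. The protocol ties a directional question to a comparison of groups formed after baseline and sets no time order between improvement and smoking change. If smoking less leads to better reported sleep or fewer symptoms, treated participants who cut down first could be counted as support.

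The size cannot be found from the document. Under the assumed central rates, with half treated, the gap is about 4 to 8 percentage points; letting the share who cut down run from 10% to 30% widens this to about 2 to 10. With no reverse effect it is zero. The gap of 6 to 13 points that follows from ignoring untreated participants does not fit the protocol's own grouping.

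A reader might also infer that a time-ordered comparison would justify saying that improvement reduces smoking. It would not. The groups are not randomised and differ in receipt of treatment, and ordering removes only one of the ambiguities.

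**What to change.** Keep the planned comparison and add a time-ordered one to the protocol, using data already collected:

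1. Classify improvement at the 3-week contact.
2. Compare the change in smoking from 3 weeks to 6 months between those improved and not improved at 3 weeks, adjusting for baseline and 3-week smoking.
3. Tabulate separately those who had already changed their smoking by 3 weeks. An early quitter may still be classed as improved at 3 weeks, and only the outcome window changes.
4. Word both results as associations.

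The cost is a few sentences of protocol text, one further analysis and one table, with no new contact and no change to care. There are downsides. Smoking reductions before 3 weeks do not count in the ordered comparison. Late responders are classed as not yet improved. Changes in both between 3 weeks and 6 months remain unordered. The direction of any remaining bias is not known, so the ordered result should not be described as conservative.

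### Improvement, which forms the groups for the smoking comparison, is fixed only as a direction of change, so the contrast may be biased either way

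*Protocol*

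**What the plan says.** All but one of the relevant statements are in the Protocol, Research Design and Methodology.

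- The rule: "Improvement is defined as better sleep quality and reduction of initial symptoms". Both components are required. Neither has a scale or a minimum change.
- Its use: "Correlation will then be made between the group that improved on treatment and the group that did not". The second group pools participants whose treatment did not work with those who had none. The purpose is "to see if improvement reduces smoking tendency with alleviated vasovagal symptoms".
- Its timing: participants with a positive sleep study are "assessed for improvement on treatment, and be questioned regarding smoking and vasovagal symptoms again", at 3 weeks and again at 6 months. The text does not say which of the two contacts decides the group.
- The mode of contact, under Data Collection: "Follow up at 3 weeks and 6 months will be done either in the clinic or over the phone and Email". No repeat sleep study is described.

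Sleeping habits and sleep apnoea symptoms are asked about at entry, but the text does not say that they are scored. Disease severity, by contrast, is graded on the apnoea-hypopnoea index in numeric bands (5-15, 15-30 and above 30 events per hour).

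**The concern.** The smoking comparison depends on who is placed in which group. A rule that asks only whether things are better turns a noisy self-report into a yes/no split at zero change, where small fluctuations matter most. The requirement that both components be better adds the opposite error: a clear gain on one component, with the other unchanged, counts as no improvement.

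The grouping variable and the outcome also come from the same person at the same contact, and no separation between the two is described. A participant who feels well, or who wants to give a good account, may report both better sleep and less smoking. The classification error would then be tied to the outcome. At stake is whether a difference in smoking between the groups, or its absence, can be read as evidence about improvement.

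**Working it through.** The Protocol gives no sample size, effect size or error rate, so there is no figure of its own to reproduce. Every input below is an assumption chosen to show a range.

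**1. False-improved rate among treated participants with no true change.** With symmetric noise and no ties, each component looks better with probability 0.5. Both look better with probability f = 1/4 + arcsin(ρ)/(2π), where ρ is the correlation between the two changes.

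- ρ = 0: f = 0.250
- ρ = 0.5: f = 0.250 + 0.5236/6.2832 = 0.333
- ρ = 0.9: f = 0.250 + 1.1198/6.2832 = 0.428

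If half of the answers are no change, each component looks better with probability 0.25. Two independent components then give 0.25² = 0.0625, about 6%.

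**2. Errors unrelated to smoking.** The observed difference is the true difference times k = PPV + NPV − 1, where p is the share truly improved and Se the sensitivity:

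- PPV = p·Se / [p·Se + (1−p)·f]
- NPV = (1−p)(1−f) / [(1−p)(1−f) + p(1−Se)]

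Sensitivity is set at 0.8-0.9, because requiring both components also misses some true improvers.

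Low end (Se 0.8, f 0.43, p 0.4): PPV = 0.32/0.578 = 0.554; NPV = 0.342/0.422 = 0.810; k = 0.364.

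High end (Se 0.9, f 0.25, p 0.6): PPV = 0.54/0.64 = 0.844; NPV = 0.30/0.36 = 0.833; k = 0.677.

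| f | Se 0.8, p 0.4-0.6 | Se 0.9, p 0.4-0.6 |
|---|---|---|
| 0.25 | 53-55% | 62-68% |
| 0.43 | 36-39% | 48-55% |
| 0.0625 (ties) | 71-77% | 82-84% |

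Without ties, about 36-68% of the true difference stays visible.

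**3. Untreated participants.** On the plain reading they belong to the non-improved group whatever they report. If half of those with no true change were untreated, the effective rate would halve to 12.5-21.5%. With the same Se and p, k is then 57-78%.

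**4. Errors related to smoking.** Take Se = 1 and no true difference, with 20% cutting down in each true group. Suppose participants with no true improvement are called improved in 60% of cases if they cut down and in 20% if they did not. With p = 0.5:

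- Classed improved: 0.5 + 0.5(0.2×0.6 + 0.8×0.2) = 0.64, of whom 0.10 + 0.06 = 0.16 cut down, or 25.0%.
- Classed not improved: 0.36, of whom 0.5×0.2×0.4 = 0.04 cut down, or 11.1%.
- Observed difference: 13.9 points, where the truth is 0.

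With p = 0.3 the observed difference is 29.0 − 11.1 = 17.9 points. A true difference of 20 points (30% v 10%) appears as 22.9 points (p = 0.3) or 23.8 points (p = 0.5).

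**The case against.** The strongest reply is that scale, cut-off and deciding visit are often left to a statistical analysis plan or a data-collection form, and neither is shown. That is fair for the name of the instrument and for the visit. It does not dispose of the point, because the Protocol does fix a rule. Followed as written, that rule counts any favourable shift on both components. A baseline score that was not collected also cannot be added later.

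A reader might go further and infer that many participants are misclassified and that the smoking contrast is therefore diluted. The document supports neither step:

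- It gives no error rate. A one-component calculation, which puts 50% of unchanged participants in the improved group, ignores that both components must be better. The two-component rate is lower, and lower still if many answers are no change.
- Untreated participants fall in the non-improved group, so chance fluctuation does not move them.
- Regression to the mean after referral at a bad time would raise the rate, but nothing in the document allows it to be sized.
- Dilution follows only if the errors are unrelated to smoking. Both reports come from the same contacts, so the bias could as well run away from zero.

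It could also be said that the Protocol lists the improvement assessment before the smoking questions. It does, but it does not lay this down as a required order, and correlated reporting by the participant does not depend on order. Finally, no primary objective is designated in the text shown. The point concerns the smoking comparison and does not touch the comparison of facial discoloration with sleep-study result.

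**Conclusion.** The concern holds as a weakness of design in the smoking comparison. The grouping rule is a bare direction of change on two components, with no minimum and no scored baseline described, and it is judged at the same contacts as the outcome. It is open to error both ways, and the resulting bias has no known direction.

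The size is illustrative only. Without ties, and with errors unrelated to smoking, 36-68% of the true difference would remain visible. Ties or a large untreated share would make the loss smaller. With correlated reporting, a true difference of zero could appear as about 14-18 points. All of these figures rest on assumed error rates, sensitivities, shares truly improved and correlations. They show that the rule can matter, not how much it will matter in this cohort. The change is worth making before enrolment, because it is cheap and the baseline cannot be recovered afterwards.

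**What to change.** Score sleep quality and sleep apnoea symptoms with the same short self-report scale at baseline, 3 weeks and 6 months, and complete it before the smoking questions at each contact. Name one visit, and use the change in score from baseline to that visit as the main explanatory variable for smoking. Keep improved versus not improved as a secondary category, with a minimum change set in advance and a stated rule for a gain on one component only.

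The cost is a few extra minutes at contacts already planned. A self-report scale can be completed in clinic, by phone or by email, and treatment is unaffected. The change will not remove correlated self-report altogether. It does replace the split at zero with a graded measure, and it keeps the smoking answer from colouring the assessment of improvement at that contact.

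### Smoking change is compared across groups defined by improvement after baseline, so the contrasts can differ with no effect of sleep apnoea or its treatment

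*Protocol*

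**What the plan says.** All of this is in the Protocol, Research Design and Methodology.

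- **Grouping of positives.** The main contrast is worded "Correlation will then be made between the group that improved on treatment and the group that did not". The second group is formed "whether due to ineffective treatment or not receiving treatment at all", so it pools treatment failures with people who were never treated.
- **What improvement means.** "Improvement is defined as better sleep quality and reduction of initial symptoms". It rests on symptoms; no threshold or repeat objective measure is named.
- **When it is measured.** At 3 weeks and 6 months positives are to be "assessed for improvement on treatment, and be questioned regarding smoking and vasovagal symptoms again", so improvement and smoking are recorded at the same contacts.
- **Negatives.** "Participants with negative results will also be followed up with and asked about their smoking habits and vasovagal symptoms". No improvement assessment is described for them.
- **Use of the negatives.** The same sentence goes on: "and compared with participants with negative sleep study results for any change in smoking habits as well".
- **Intended inference.** The stated purpose is "to see if improvement reduces smoking tendency with alleviated vasovagal symptoms", which is a causal reading.

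Under Ethical Considerations, the Protocol adds that the study observes the treatment plan and does not change it, so treatment is not assigned by the study.

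**The concern.** Improvement is not a baseline characteristic or an assigned treatment. It is an outcome, collected alongside the smoking outcome, and it sorts the positives by how they fared. The negatives are left whole, so they mix people who fared well with people who fared badly.

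Several ordinary mechanisms would link improvement with smoking less without one causing the other:

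- a motivated or generally healthier person does better on both;
- a person inclined to give favourable answers does so on both questions at one interview;
- cutting down smoking may itself ease symptoms, which reverses the causal direction the protocol has in mind.

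Any of these pulls improved positives up and not-improved positives down. The negatives look like an outside check on that contrast, but an improved subset set against an unselected group inherits part of the same distortion. What is at stake is the study's stated conclusion about smoking: a difference of this kind could be read as showing that improvement reduces smoking.

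**Working it through.** The Protocol gives no sample size, effect size or error rate for this comparison, so there is no figure of its own to reproduce. The check asks what the planned contrasts would show if there were no effect at all. Every numerical input below is an assumption.

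**1. Illustration with proportions.** Suppose 20% of all positives and 20% of negatives cut down, so that positives and negatives do not differ. Half of the positives improve. Let p1 and p0 be the proportions cutting down among improved and not-improved positives. Then:

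- (p1 + p0)/2 = 0.20, so p0 = 0.40 − p1;
- [p1/(1 − p1)] / [p0/(1 − p0)] = OR, the odds ratio produced by shared causes.

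Substituting gives (OR − 1)p1² − (1.4·OR + 0.6)p1 + 0.4·OR = 0. For OR = 2.5 this is 1.5p1² − 4.1p1 + 1 = 0, so p1 = (4.1 − √10.81)/3 = 0.271 and p0 = 0.129. Check: the odds are 0.372 and 0.148, with ratio 2.5.

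| OR | Improved | Negatives | Not improved | Improved minus negatives | Improved minus not improved |
|---|---|---|---|---|---|
| 1 | 20.0% | 20% | 20.0% | 0 points | 0 points |
| 1.5 | 23.2% | 20% | 16.8% | 3 points | 6 points |
| 2 | 25.4% | 20% | 14.6% | 5 points | 11 points |
| 2.5 | 27.1% | 20% | 12.9% | 7 points | 14 points |
| 3 | 28.3% | 20% | 11.7% | 8 points | 17 points |

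**2. A second model, on a continuous scale.** Let smoking reduction (in SD units) and a latent improvement score have correlation ρ among positives, label the top share p as improved, and give negatives the same mean and SD as all positives. With c = z(1 − p) and φ the normal density, the expected gaps are:

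- improved minus negatives: ρφ(c)/p;
- not improved minus negatives: −ρφ(c)/(1 − p);
- improved minus not improved: ρφ(c)/[p(1 − p)].

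The first gap is thus (1 − p) times the third, so the distortion against negatives is always the smaller one. At ρ = 0.3 and p = 0.5 the gaps are 0.24, −0.24 and 0.48 SD.

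False-positive rates of a two-sided 5% test were simulated (4,000 replicates, 100 positives and 100 negatives, p from 0.3 to 0.7):

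| ρ | Improved v negatives | Improved v not improved |
|---|---|---|
| 0 | about 5% | 5–6% |
| 0.2 | 10–21% | 34–35% |
| 0.3 | 16–41% | 64–70% |
| 0.5 | 40–83% | 98–99% |

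**3. The unselected contrast under the same null.** With all positives kept together against all negatives, the rate was 4.2% to 5.8% in every scenario run, including those with 200 positives.

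Neither model represents the untreated patients separately. Both treat the split as one on course alone.

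**The case against.** Five points can be made on the other side.

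- **The text is less definite than it may seem.** A reader might infer that each part of the positives is tested separately against the negatives and that a pooled comparison is ruled out. The clause does not say so. Its grammatical subject is the improved and not-improved groups, and no pooled comparison on smoking is described, but silence in a short protocol is not exclusion, and an analysis plan could add one. This stands. What remains is that the protocol itself names the groups, the comparator and the causal aim, which is more than a detail left for later.
- **The split is partly by treatment.** Untreated patients fall in the second group as the text is written, so it is not purely a selection on course. This stands. It adds confounding by receipt of treatment and does not remove the problem.
- **Other unselected contrasts exist.** A reader might take all positives v all negatives as the sole contrast free of this selection. It is not: baseline AHI grade is recorded and also involves no selection on improvement.
- **The pooled contrast answers a different question.** It concerns sleep apnoea status under usual care and dilutes any effect confined to those who improve. Suppose negatives 20%, improved 35%, not improved 20%, half improving, 100 per group (assumed). The pooled contrast is 27.5% v 20%, SE = √(0.275·0.725/100 + 0.20·0.80/100) = 0.0600, z = 1.25, power about 24%. Improved v negatives has SE = √(0.35·0.65/50 + 0.20·0.80/100) = 0.0784, z = 1.91, power about 48%. Requiring a pooled difference before giving any weight to the other contrasts could therefore discard a real effect, and is not recommended.
- **The size is conjecture.** True: with no link between improving and cutting down, there is no bias.

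**Conclusion.** The concern holds as a matter of design. The Protocol defines the positive groups by a symptom-based status known only after baseline, describes the comparison with unassessed negatives through those groups, and gives the result a causal reading. Any shared cause, shared reporting or reverse causation can then produce a difference with no effect of sleep apnoea or treatment. The larger distortion is in the main contrast, improved v not improved; the contrast with negatives is affected to a lesser degree.

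On the assumed inputs (20% cutting down, half improving, odds ratio 1.5 to 3) the spurious gaps are about 6 to 17 points and 3 to 8 points respectively, and nil at an odds ratio of 1. The document fixes none of these inputs, so it supports the mechanism but not its size.

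A reader might also infer that the order improved, then negatives, then not improved is bound to appear and be taken as confirmation. The document does not support that: it states no decision rule about such an ordering, and the ordering depends on a link whose strength is unknown.

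**What to change.** Add to Research Design and Methodology:

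1. Change in smoking is also compared between all positives and all negatives, and between positives by baseline AHI grade and all negatives, adjusting for baseline smoking.
2. The improved v not-improved and improved v negatives contrasts are reported as association only, and not as evidence that improvement reduces smoking.

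The data are already planned: smoking habits are taken in the initial history and asked about again at follow-up in both positives and negatives, and AHI is graded from the sleep study. The wording of the aim should be brought into line with point 2.

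The cost is a sentence or two and a further comparison. That comparison is diluted if few positives are treated, and it remains observational, so it removes the selection on improvement but not other confounding between positives and negatives.

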### *Population and Sample*

A purposive sampling technique will be utilized to determine the study population. The target population is patients above the age of 18 referred for sleep study at the Jordan University Hospital and Jordan Hospital. Patients who agree to participate in this study and sign the consent form.

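### The named comparison does not show whether smoking falls in the same people whose vasovagal symptoms are relieved, and it is not limited to people who have such symptoms at baseline

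*Protocol*

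**What the plan says.** All of the following is in the Protocol; the first four points are under Research Design and Methodology.

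- **Question and contrast.** "Correlation will then be made between the group that improved on treatment and the group that did not", the purpose being "to see if improvement reduces smoking tendency with alleviated vasovagal symptoms". Participants with negative sleep studies are then compared for change in smoking habits; vasovagal change is not named in that second comparison.
- **Grouping variable.** "Improvement is defined as better sleep quality and reduction of initial symptoms". Vasovagal symptoms are not named in this definition.
- **Not-improved group.** It pools two kinds of patient: "whether due to ineffective treatment or not receiving treatment at all".
- **Data.** At baseline, "participants will be asked in detail about their smoking habits, vasovagal symptoms, sleeping habits, and any specific obstructive sleep apnea symptoms". At 3 weeks and 6 months those with a positive study will "be questioned regarding smoking and vasovagal symptoms again". Negatives are also asked both items at follow-up, at a time not stated.
- **Entry** (Population and Sample). "The target population is patients above the age of 18 referred for sleep study", with consent. Neither vasovagal symptoms nor smoking at baseline is required, and no comparison is restricted to people who have either.

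**The concern.** The question joins two changes: less smoking, together with relief of vasovagal symptoms. The contrast named to answer it groups people by a third variable, improvement. The improved group may smoke less and may also have fewer vasovagal symptoms while those changes occur in different people. Two group differences side by side do not show that the changes go together.

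In addition, someone without vasovagal symptoms at baseline cannot have them relieved, and a non-smoker cannot cut down. Both kinds of participant may sit in either group, and they dilute any link that exists.

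At stake is what the study can conclude. It could present an accompanying vasovagal change as if it had been examined together with smoking, or fail to see a real link because the people to whom the question applies are averaged with people to whom it does not.

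**Working it through.** The protocol states no sample size, rate or effect, so there is no figure to reproduce. Every rate below is an assumption.

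**1. Can the named contrast tell a link from no link?**

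Assume 60% have vasovagal symptoms at baseline, and that among them relief occurs in 60% of the improved and 20% of the not-improved. Relief across each whole group is then:

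- improved: 0.60 × 0.60 = 36%
- not improved: 0.60 × 0.20 = 12%

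*Linked.* A smoking cut occurs in 50% of people with relief and 10% of people without:

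- improved: 0.36 × 0.50 + 0.64 × 0.10 = 24.4%
- not improved: 0.12 × 0.50 + 0.88 × 0.10 = 14.8%

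*Not linked.* Suppose instead that a cut occurs in 24.4% of the improved and 14.8% of the not-improved, whatever happens to their vasovagal symptoms. Relief stays at 36% v 12%.

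| Quantity | Linked | Not linked |
|---|---|---|
| Smoking cut, improved v not improved | 24.4% v 14.8% | 24.4% v 14.8% |
| Vasovagal relief, improved v not improved | 36% v 12% | 36% v 12% |
| Cut, relieved minus not relieved, symptomatic, within each improvement group | 50 − 10 = 40 points | 0 points |
| Cut, improved minus not improved, no baseline vasovagal symptoms | 10 − 10 = 0 points | 24.4 − 14.8 = 9.6 points |

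The first two rows are what the named contrast yields, and they are identical. The last two rows separate the cases.

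If sparse cells force pooling over improvement groups, the unlinked case no longer gives exactly zero. With half of patients improving, the relieved are 0.6/(0.6 + 0.2) = 75% improved, and the not-relieved are 0.4/(0.4 + 0.8) = one third improved. Cuts are then 0.75 × 24.4 + 0.25 × 14.8 = 22.0% and (24.4 + 2 × 14.8)/3 = 18.0%, a 4-point difference with no link. A pooled table therefore needs that caution.

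**2. How much is a real link diluted?**

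Difference seen = prevalence of baseline vasovagal symptoms × (relief rate in improved − relief rate in not improved) × effect of relief on smoking.

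Take a 20-point effect and full relief in symptomatic improved patients:

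| Prevalence | No relief in not-improved | 20% relief in not-improved |
|---|---|---|
| 10% | 0.10 × 1.0 × 20 = 2 points | 0.10 × 0.8 × 20 = 1.6 points |
| 30% | 0.30 × 1.0 × 20 = 6 points | 0.30 × 0.8 × 20 = 4.8 points |
| 50% | 0.50 × 1.0 × 20 = 10 points | 0.50 × 0.8 × 20 = 8 points |

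The figure depends on the relief rate assumed in the not-improved group, so that rate must be stated with it.

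On the rates of step 1 the difference is prevalence × 0.40 × 40 points: 16, 9.6, 4.8 and 1.6 points at 100%, 60%, 30% and 10% prevalence. The standard two-proportion formula (80% power, two-sided 5%) then needs 117, 268, 858 and 6,287 per group.

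**The case against.** The strongest objection is scope. Only the protocol is at hand, and a cross-tabulation within a subgroup is the kind of detail a SAP may supply. Both items are recorded for each person before and after, so nothing in the design prevents it. That stands as far as it goes: it would be wrong to say that the study cannot link the two changes. It does not remove the point, because the protocol itself names the contrast and states what it is meant to show, and the two do not match.

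Second, a reader might infer that the protocol sets out to prove that smoking falls *because* vasovagal symptoms are relieved. The text says *with*, not *because*, and nowhere states that two group differences will be taken as proof of a mechanism. That stands. But smoking falling together with vasovagal relief is still a statement about joint change in the same people.

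Third, the symptoms in the improvement definition may include vasovagal ones. If so, relief is partly built into the grouping and a vasovagal difference between groups is partly automatic. It is still not tied to smoking.

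Fourth, a reader might take the diluted difference to be a wrong answer. It is not: it is a valid average effect of improvement in the referred population. What is lost is sensitivity to the vasovagal part of the question, and with no sample size given that loss cannot be judged in absolute terms.

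Fifth, the added table could be oversold. Relief is not randomised, it arises after baseline, and it is asked at the same contacts as smoking. Relief lowering smoking, less smoking relieving symptoms, and a shared cause all look alike. This stands in full and limits what the fix may claim.

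**Conclusion.** The point holds in limited form. The comparison named in Research Design and Methodology does not examine whether smoking falls in the people whose vasovagal symptoms are relieved, and it is not restricted to people who have such symptoms at baseline. The documents do not support the stronger readings: that a causal pathway is claimed, that the data cannot link the two changes, or that the improved v not-improved contrast is invalid.

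The size is illustrative only. On the assumed rates, the group results are the same with and without a within-person link (24.4% v 14.8%), while the comparison within persons, inside improvement groups, differs by 40 points against none. At 30% prevalence and a 20-point effect, with full relief in the improved, the group contrast would show 6 points if none of the not-improved get relief and 4.8 points if 20% do. The share of participants without vasovagal symptoms is not given; that they are included follows from the absence of any restriction.

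**What to change.** 1. Keep the improved v not-improved contrast, and describe it as the average effect of improvement on smoking.
2. Add, among baseline smokers with vasovagal symptoms at baseline, a cross-tabulation of change in smoking by vasovagal relief (yes or no). Show it by improved, not-improved and negative group where numbers allow, and otherwise pooled, noting that pooling mixes in the effect of improvement itself. Fix in advance what counts as relief and as a change in smoking.
3. Show baseline smokers without vasovagal symptoms separately. A similar fall in smoking among improved patients in this group would count against a vasovagal explanation.
4. Report the table as a within-person association. Do not conclude from two separate group differences that vasovagal relief accompanies or explains reduced smoking. State that the table can count against the explanation or be consistent with it, but cannot establish it.
5. Where dilution figures are quoted, state the relief rate assumed in the not-improved group.

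**Cost.** No new visits, questions or change in care: both items are already asked at baseline and follow-up in positives and negatives. The price is a smaller subgroup. Relief (yes or no) by three groups gives 2 × 3 = 6 strata, some possibly very sparse, so estimates may be imprecise.
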